#### 14.3.5 Monitoring Participant for Comfort

All participants will be arousable during surgery and thus able to vocalize any discomfort. Our institution has a specially trained anesthesia team adept at deep brain stimulation surgery and its particular nuances as it pertains to awake procedures. Patients will all be on a Precedex drip for sedation with intermittent dosing of remifentanyl for comfort.

The second surgery for generator internalization involves general anesthesia, skin incision and subcutaneous manipulation. Due to these factors (superficial post-operative pain, incomplete recovery from anesthesia), the subject may not be in a satisfactory state to be discharged on the surgery day, especially if scheduling factors cause a late surgery. Physician judgement will be used to decide whether an additional 1-2 days of in-hospital observation is appropriate.

Subjects or investigator-clinicians can request and carry out an additional unscheduled in-person visit to study sites at any time. This will be done if the subject has any perceived safety issues, or requests a change in stimulation parameters to improve pain control.

#### 14.4 Lead and or DBS Removal

These devices have been designed and tested, with FDA approval for certain disorders, to be permanent implants. However, there are occasions in which the device or a portion of the system might need to be removed. If necessary, this requires additional surgery with risk.

The most common reason for removal is infection. At our institution, deep brain stimulation carries a 1.5% risk of infection necessitating removal. The majority of the time, the implantable neurostimulator and extension cables need to be removed with preservation of the intracranial lead. This is a result of the fact that most infections start at the neurostimulator implant site.

Alternative reasons for removal of the system would be patient request in the event that the device does not produce its intended results. However, in this instance, it is rare for patients to request removal as it requires additional surgery and there is no significant risk to keeping the device. Devices may also malfunction or break necessitating removal or revision surgery to fix.

Generators have a lifespan which ends at the time of battery failure. On average generator batteries fail after 3-5 years depending on stimulation parameters. Battery longevity depends also on sensing features. Thus it is expected that the battery of the Activa PC+S 37604 Neurostimulator will last less than that of the Activa PC 37601 (which does not allow for sensing). When considering the stimulation parameters currently being used in the study, the Medtronic reference manual for battery longevity of the Activa PC+S neurostimulation system for DBS estimates the longevity at roughly over 4.5 years. This number only represents an estimate, considering battery longevity depends on several factors: programmed parameters, system impedance, hours per day of stimulation, degree of patient control over programmable stimulation parameters, and the use of sensing features (in the case of the Activa PC+S system). This figure is based on stimulation frequencies >100 Hz as used in movement disorders; it is expected that pain treatment will use lower frequencies (<25 Hz) which will give at least 1-2 years more lifetime according to calculations based on manufacturer's confidential data (M949908A001, System eligibility and battery longevity manual for Activa PC+S). In the event that battery replacement would be needed, routine, same day, surgery is performed to remove and replace the generator.

#### 14.5 Post Implantation Procedures & Follow-up

Procedures performed to evaluate the safety of the investigational procedures and to evaluate subject outcome for this study include:

- A. Beginning one week after surgery, participants will undergo follow-up assessments post-implantation:
  - i. Pain assessments every 2 weeks (ISCI basic pain data set, NPSI), starting on week 10, will assess for development of, or changes in neuropathic pain; more comprehensive pain testing (MPI quantitative sensory testing/allodynia) will take place on comprehensive testing visit weeks (20-week, 32-week, and 52-week).
  - ii. Autonomic Standards Assessment: on on-site visit weeks (BP, HR, sympathetic skin response) and on week 20, week 32, and week 52 (Tilt table response exam). Patient Self-assessment of Autonomic Responses occurs weekly starting on week 3, except on on-site visit weeks.
  - iii. QoL assessments: on on-site visit weeks, starting on week 12 (Beck Depression Inventory (BDI-1a)) and weekly, starting on week 9 (Guy/Farrar Patient Global Impression of Change (PGIC));
  - iv. ASIA motor and sensory assessments: on weeks 20, 32 and 52 to assess any improvement or deterioration in neurological function;
  - v. a qualitative exit interview with audio recording at 52 weeks, giving subject and investigators will be given the opportunity for open comments and questions concerning elements of the study.

- B. Follow-up assessments will take place either at the Miami VA Hospital or at The Miami Project to Cure Paralysis, Department of Neurological Surgery, for regular follow-up visits for 44 weeks post-surgery. At each visit, information will be collected regarding the safety of the treatment, the presence or absence of adverse side effects, and the efficacy of the therapy with respect to recovery of neurological functioning or the development of adverse effects.

#### **14.6 Medication(s)/Treatment(s) Permitted (Concomitant Medications) and not Permitted Before and/or During the Trial:**

##### A. Permitted Treatment

All medication taken by the participant during the study is to be recorded. All medications required to treat the participant should be administered as recommended. The following data will be recorded for all included participants up to the end of the study period: name of drug or nature of treatment, start and end dates, hours of administration, and indication. Fluid and blood replacement will be measured and documented on a daily basis. Additionally, any therapeutic or surgical procedure performed during the study period should be recorded, including the date, description of the procedure, and clinical findings

##### B. Prohibited Treatment

Investigational drugs and any other intervention (not part of the guidelines for management of SCI) known to have a potential impact on outcome are prohibited.

#### **14.7 Procedures for Monitoring Participant Compliance**

(Please Refer to Section 20 QUALITY CONTROL and QUALITY ASSURANCE)

### **15 SAFETY**

Participants will be continuously monitored throughout a one (1) year evaluation period. Assessments will be performed as outlined in Table 1 and Table 2 in section 13.6. Assessments will also include monitoring of occurrence of AEs (acute, delayed, and/or cumulative), as well for changes in clinical status, neurological status and/or functional status. Safety will be determined as follows:

- a) Adverse events or other safety concerns will be ascribed to one of two categories: (1) general known problems with all types of DBS (e.g. infection) or with untreated SCI (e.g., bladder control failure); (2) problems caused by the PAG/PVG site in particular (e.g., hypotension) or to a specific response of SCI symptoms to DBS (e.g., more pain). The first category will not lead to ejection of the method. The second category can be evaluated more by turning off the stimulation or examining correlations with the 4-week periods of (8-weeks after week 24) adjustment of stimulation amplitudes. Second-category events will be carefully assessed and will lead to discontinuation of the study treatment if they cannot be ascribed to special circumstances in a given patient.
- b) Comprehensive pain, motor and autonomic assessment will occur on screening and enrollment (baseline) and then on on-site visit weeks (weeks 12, 16, 20, 24, 32, 40, 48 and 52).
- c) The correct functioning of the DBS apparatus will be monitored every 4 weeks, after implantation, until week 24. Thereafter this assessment occurs every 8 weeks, and on the last visit (week 52).
- d) Pain Assessments using the ISCI-PDS:B and neuropathic rating scale will evaluate development of neuropathic pain syndromes.

The secondary hypothesis which concerns autonomic assessment will also take place during routine patient visits. Heart rate, blood pressure, sweating, body temperature and breathing will be classified as normal, abnormal, unknown, or unable to access. Within the abnormal category, sub-categories will be

specified: for heart rate, bradycardia, tachycardia or other dysrhythmias; for blood pressure, systolic blood pressure under 90 mm Hg, orthostatic hypotension, autonomic dysreflexia; for sweating, hyperhidrosis above lesion, hyperhidrosis below lesion, hyperhidrosis below lesion; for body temperature, hyperthermia, hypothermia; for breathing, requiring full ventilatory support, requiring partial ventilatory support, impaired not requiring ventilatory support. Lower urinary tract, bowel and sexual function will be scored on the following: awareness of need to empty bladder and ability to prevent urine leakage; sensation of need for bowel movement, ability to prevent stool leakage, voluntary anal sphincter contraction; genital arousal (psychogenic and reflex), orgasm, ejaculation (male), and sensation of menses (female).

Comprehensive testing sessions will analyze vagal and sympathetic influences on the cardiovascular system, measuring blood pressure and heart rate variability (power spectrum analysis) during sit-up or tilt-table challenge. However, if a subject is not able to tolerate the tilt table response exam to completion, he/she will not be required to fulfill this test at subsequent visits. The neurologist will decide whether it is recommended for subjects to undergo this assessment thereafter. Additionally, the test will not be required for subjects not expected to show autonomic dysreflexia because of their lower level of injury, as determined by the neurologist.

Assessment of motor and non-pain somatosensory function will be done during visits every 4 weeks. Clinical sensory testing will include Light Touch and Pin Prick tests defined in the ASIA standards [1]. The Beck Depression Inventory (BDI-1a) will also be used, to assess emotional function in neuropathic pain [4]. A score of 30 or above indicates severe depression. If BDI assessment suggests suicidal thoughts, the Columbia Suicide Severity Rating Scale will be used in consultation with a clinical psychologist.

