Device Implant Procedure	
Participants presenting to the trial site with a history and mechanism consistent with chronic SCI with neuropathic pain below the level of injury, will be assessed using defined screening tests. Eligible participants will also undergo a multi-step consent process.
 
Upon successful consent, trained and certified study personnel will perform imaging and neurological systems exams. The neurological systems exams will be utilized as the baseline measure of neurological status including neuropathic pain and autonomic dysreflexia.
 
Upon successful completion of screening and baseline measurements, participants will undergo surgery to implant unilateral or bilateral DBS Leads (Model 3387S), extensions (Model # 37085 or 37086) and implantable neurostimulator (IFN) (Model 37601, or Model 37604).
 
After successful implantation and one week recovery, subjects will participate for 44 weeks in the study.

Treatment group	
Single treatment group. Ethical considerations forbid a control group that receives implant surgery without stimulation. Hence participants must serve as their own controls.

Frequency	
One-time implantation of Activa PC or Activa PC+S Deep Brain Stimulation device system. Continuous stimulation, or cycled in 12-hour on/off periods, or in shorter on/off periods, for ~ 40 weeks. Voltage range 0.1-10V.

Safety Evaluation	
 
1) Although preclinical data and clinical experience suggests DBS and device implantation is relatively safe, several adverse events are possible and will be noted,
 
2) Comprehensive pain, motor and autonomic assessment will occur on screening and enrollment (baseline) and then at every on-site visit week throughout the study.
 
3) The correct functioning of the DBS apparatus will be monitored at 4-week intervals after implantation until study week 24, and at 8-week intervals thereafter.
 
4) Pain Assessments using the ISCI-PDS:B will evaluate development of neuropathic pain syndromes.
 

Secondary outcomes	
 
1) Tilt table response exam
 
2) Autonomic Standards Assessment (BP, HR, sympathetic skin response)
 

Safety Analysis Plan	

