Urine Pregnancy (note 4)	2		x					x								
HIV, Hep B, Hep C serology	1		x													

1 All General Assessments and Neurological System Exams, i.e., BDI, MMSE, QST, Pain (ISCI PBDS, NPSI, MPI-SCI), PGIC, during this period will occur prior to DBS adjustments.

2 Pain testing may take place at either site

3 Not required if determined subject can't tolerate it to completion

4 Urine pregnancy test for premenopausal women

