### 17.4 Missing Data

Although every attempt will be made to avoid missing outcome data, missing data is anticipated with any longitudinal study. The missing data can be defined as intermittent or dropout. Although every effort will be made to prevent participants from missing visits or dropping out of this study, it is possible that some of the measurements planned over the 52 weeks will be missing. The impact of missing data will be examined by comparing means and standard deviations for participants that have and do not have the relevant missed visit data. The reason for missing data will be fully examined to confirm this assumption.

Missing data will be imputed using regression methods.

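### Later tilt tests can be waived because an earlier one was not tolerated, but missing data are regression-imputed and non-completion is never counted as a result

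*Combined protocol and SAP*

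**What the plan says.** - **Status of the test.** The synopsis (section 3) lists "Tilt table response exam" first of two secondary outcomes. Section 16 includes the tilt response among the efficacy-trend parameters. Section 17.1 names a tilt-derived heart rate measure as an example of a normally distributed variable for its generalized linear models.
- **Schedule.** Section 14.3.1 places one test at baseline (week 2). Table 1 and section 14.5 place the others at weeks 20, 32 and 52.
- **Waiver for intolerance.** Section 15 says that a participant "not able to tolerate the tilt table response exam to completion, he/she will not be required to fulfill this test at subsequent visits". Note 3 to Table 2 repeats this: "Not required if determined subject can't tolerate it to completion". Section 15 adds: "The neurologist will decide whether it is recommended for subjects to undergo this assessment thereafter".
- **Waiver for injury level.** In the same paragraph, "the test will not be required for subjects not expected to show autonomic dysreflexia because of their lower level of injury", again as judged by the neurologist.
- **Manoeuvre.** Section 15 describes comprehensive testing as "measuring blood pressure and heart rate variability (power spectrum analysis) during sit-up or tilt-table challenge".
- **Missing data.** Section 17.4 states: "Missing data will be imputed using regression methods". It also compares participants with and without the missed data and examines the reasons. It attaches no analysis rule to what is found.
- **Harm of interest.** Section 15 a) defines a class of "problems caused by the PAG/PVG site in particular (e.g., hypotension") that can lead to discontinuation of study treatment.

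**The concern.** Being unable to finish a tilt test is itself an unfavourable orthostatic result. Under the plan it can be the reason why later values are absent, so the missingness is informative by design. A regression can only learn the tilt response from tests that were performed, and at later visits those come mainly from people who tolerated the test. Unless its predictors carry the intolerance, it will give the waived participants tolerant-looking values. Section 17.4 also does not separate tests waived for intolerance from those waived for lower injury level, which are absent for an unrelated reason.

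At stake is whether the tilt summary at weeks 32 and 52 can be read at face value. Hypotension is the protocol's own example of a site-specific problem, and with at most 12 participants one or two waived cases can move the group mean. A reassuring tilt summary could then contradict the adverse event listing in the same report.

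**Working it through.** **1. The plan's own count.** Table 2 gives 4 tilt tests per participant. One baseline test plus weeks 20, 32 and 52 gives 1 + 3 = 4, so the figure reproduces. For 12 participants that is 12 × 4 = 48 planned tests, of which 12 × 3 = 36 follow implantation.

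**2. What the waiver can remove.** It covers only visits after the failed test.

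| First failure | That test | Later tests that may be waived |
|---|---|---|
| Week 2 (before DBS) | performed | 3 (weeks 20, 32, 52) |
| Week 20 | performed | 2 (weeks 32, 52) |
| Week 32 | performed | 1 (week 52) |
| Week 52 | performed | 0 |

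**3. Direction of the bias.** Let k of n participants have no value at a visit because of intolerance. Let the value they would have shown be lower, by an average of E, than the value predicted from those who were tested. Then

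error in the group mean = (k/n) × E, toward no harm.

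For any E above 0 the direction is fixed. The documents give neither k nor E, nor a standard deviation for any tilt measure.

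**4. Illustration (all values assumed).** Take n = 12, E of 15 or 30 mm Hg, and no change in the others. The true mean change is -(k × E)/12, for example -(2 × 30)/12 = -5.0. A simulation with 4,000 runs per case checked this. It assumed a baseline response of mean -10 and SD 8 mm Hg, and a week-52 value of -10 + 0.5 × (baseline + 10) plus noise of SD 7. Week 52 was imputed from baseline by a regression fitted in completers.

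| k | True, E = 15 | True, E = 30 | After imputation (E = 15; E = 30) |
|---|---|---|---|
| 1 | -1.25 | -2.5 | -0.01; -0.04 |
| 2 | -2.5 | -5.0 | -0.01; -0.03 |
| 3 | -3.75 | -7.5 | -0.03; 0.03 |
| 4 | -5.0 | -10.0 | -0.01; -0.01 |

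The near-zero results follow from the assumption that completers do not change. They show the mechanism and do not estimate its size.

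**5. The same cases counted as outcomes.** With k = 1, 2, 3, 4 of 12, intolerance is 8.3%, 16.7%, 25.0% and 33.3% (exact 95% intervals 0.2-38.5, 2.1-48.4, 5.5-57.2 and 9.9-65.1). A completers-only display shows 0/11, 0/10, 0/9 and 0/8.

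**The case against.** **A reader might infer that DBS-induced orthostatic intolerance disappears from the trial.** The documents do not support that.
- A participant who first fails at week 20 is tested at week 20, and nothing says that the failure or the partial readings are discarded. A first failure at week 52 waives no later test.
- Not required is not the same as barred. The neurologist may recommend further tests, so it also cannot be said that someone intolerant at baseline can never show improvement.
- Section 15 makes orthostatic hypotension and low systolic pressure named categories of the autonomic assessment. Table 1 schedules the Autonomic Standards Assessment at on-site visits, and it is the other listed secondary outcome. Table 2 plans 12 vital-sign and 52 adverse event assessments, and section 17.1 lists all adverse events.

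**The imputation step is partly inferred.** Section 17.4 speaks of missed visits and does not say whether a permitted waiver at an attended visit counts as missing. The predictors are unspecified. If they included a participant's own failed test or orthostatic findings, the pull would be weaker. Both points stand, but they are gaps in the plan and do not protect against the bias. Examining the reasons for missingness does not help either while no rule follows from it.

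**The analysis is descriptive.** Section 17.3 says so, but section 17.1 specifies models that include a tilt variable, and imputed values distort a plain mean as well.

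**The magnitude is true by construction.** This is correct. A mean tilt systolic change is not a defined endpoint, the assumed falls have no source in the documents, and the injury-level waiver means that fewer than 12 may be tilted.

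**A reader might also infer that participants move from tilt to sit-up and that the difference would be read as change.** The text leaves this possible, but every schedule lists tilt and no rule provides for a switch.

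**Conclusion.** The point holds in a limited form. Tilt missingness can be caused by the tilt result, the general imputation rule makes no exception, and non-completion is never defined as a result. Applied literally, the plan draws the tilt summary at visits after a failure toward the values of those who tolerated the test, and so toward no harm. This rests on three assumptions: that waived tests are treated as missing under section 17.4, that the imputation model does not carry the intolerance, and that waived participants would have responded worse than predicted.

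The direction follows from these assumptions, but the size does not. The illustrative 1.25 to 10.0 mm Hg reflects assumed falls and counts only. The fault lies in one secondary outcome. The trial's wider capture of hypotension is intact, and its safety judgement does not rest on a mean tilt change. The correction is nonetheless worth making, because it is cheap and a few waived tests weigh heavily among 12 participants.

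**What to change.** Change recording and analysis only. The decision to retest stays with the neurologist, and no new challenge procedure is added.

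1. At each tilt visit, record and tabulate one status per participant: completed; stopped for intolerance, with the partial readings and the reason; waived for earlier intolerance; or waived for lower injury level.
2. Report intolerance as an outcome category at the visit where it is observed. Show later waived visits separately and do not assume that intolerance persists, since stimulation is readjusted between visits.
3. Amend section 17.4 so that tests stopped or waived for intolerance are not regression-imputed.
4. If both sit-up and tilt are used, compute change only within the same manoeuvre.

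The cost is about a sentence each in sections 15 and 17.4 and a few case report form fields for status, reason and partial readings. The drawback is that the tilt outcome becomes partly categorical, with fewer continuous values to summarise.

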## 16 ASSESSMENT OF TREND-TOWARD-EFFICACY

The trend towards efficacy of the intervention will be assessed from the following parameters:

- a. AIS upper and lower extremity motor and sensory scores.
- b. Pain Assessments: ISCI basic pain dataset, quantitative sensory testing and Self-report version of ISCI basic pain dataset.
- c. Autonomic Assessments: BP, HR, tilt table response, sympathetic skin responses,
- d. Quality of Life: Beck Depression Inventory (BDI-1a), Guy/Farrar Patient Global Impression of Change (PGIC).

## 17 STATISTICAL CONSIDERATIONS

### 17.1 Safety Analyses:

The analyses for safety will be mainly descriptive, focusing on trends for within-subject differences and changes in reported pain intensity during routine patient visits for the duration of the study. The expected outcome is stable, long-lasting change in the Pain Assessment Scale score from baseline to 44 weeks post-implant .All AEs and SAEs will be listed and their incidence compared to historical controls. The primary safety analysis will be conducted on all patient data when all 12 participants have completed the study.

